## 4 STATISTICAL METHODOLOGY

### 4.1 General Considerations

Unless otherwise specified, continuous data will be summarized descriptively by apraglutide dose group (High Dose, Low Dose, Total Randomized, Low Body Weight, Total) and by time point. Descriptive statistics for continuous variables will include: the number of subjects, mean, standard deviation (sd), median, first and third quartiles (Q1, Q3), minimum, and maximum. All raw data will be presented to the original number of decimal places. Where appropriate, mean, median, and confidence interval will be presented to one more decimal, while standard deviation will be reported to two more decimals.

Unless otherwise specified, categorical data will be summarized descriptively by apraglutide dose group (High Dose, Low Dose, Total Randomized, Low Body Weight, Total) and time point. Summary statistics for categorical variables will contain counts and percentages. The numbers and percentages of missing data for a variable will be reported when applicable. Percentages will be reported to one decimal except for zero and one hundred percent, which will be presented as 0% and 100%, respectively; unless otherwise specified, the percentages are based on the number of subjects in the respective analysis set. Two-sided 95% confidence intervals for single proportion will be estimated via Clopper-Pearson exact method.

Analyses will be performed using SAS® (version 9.4 or higher, SAS Institute Inc., Cary NC.) and/or R (version 4.1.0 or higher, R Foundation for Statistical Computing, Vienna, Austria). When possible, note that the preferred use of methods: Hyndman and Fan's Definition 2 (1996) for quantiles estimation, "half away from zero" for rounding.

#### 4.1.1 *Definition of Baseline, Analysis Visits, Visit Window*

Baseline is defined as the last measurement prior to the first administration of the trial treatment (i.e. first administration of apraglutide). The last available scheduled or unscheduled assessment collected on or before the date of start of trial treatment will be flagged as the baseline assessment. If both time of assessment and time of treatment start are captured (such as labs), the last available assessment before the treatment start date/time will be used for baseline.

For questionnaires, baseline is defined as the form completed at the baseline Visit.

Scheduled visits will be assigned to analysis visits as recorded on the electronic case report form (eCRF).

Visit windowing will not be used for handling unscheduled visits. Instead, all unscheduled visits will be assigned a visit name of “Unscheduled”. Such visits will be included in data listings and will contribute to the derivation of best- or worst-case values where applicable.

Analysis day will be calculated in reference to the date of the first administration of apraglutide. The day of the first administration of the investigational medicinal product (IMP) will be “analysis day 1”, and the day immediately before analysis day 1 will be “analysis day -1”. There will be no analysis day 0.

Each date will be assigned an analysis day calculated as follows:

- if the date < first dose date then analysis day = (Assessment date/Event date – first dose date)
- if the date  $\geq$  first dose date then analysis day = (Assessment date/Event date – first dose date) +1.

The analysis day will be used to compute duration for time-to-event endpoints.

The visit labels will correspond to the ones reported in the Schedule of Assessments. For instance, Visit Day 7 corresponds to a visit occurring at analysis day  $8 \pm 1$  day (i.e., between analysis day 7 and analysis day 9).

#### 4.1.2 *Handling of Dropouts and Missing Data*

Unless specified otherwise, missing data values will be recorded as missing and will not be imputed for the statistical analysis. Only observed data values will be used for the reporting of descriptive statistics.

Subjects with missing data such that the response, for instance the Day 56 lower GI response, cannot be determined will be included in the analysis as non-responders, consistent with intent-to-treat principle. The details for handling missing data and intercurrent events are specified in the estimand description in Section 4.3.9.2.

Censoring for time-to-event endpoint will be described for each endpoint separately.

In cases of missing or incomplete dates (e.g. AE and concomitant medications), the missing component(s) will be assumed as the most conservative value possible, taking the worst-case approach. Thus, an adverse event will be considered a treatment emergent adverse event (TEAE) unless the recorded dates conclusively prove otherwise. For example, if the start date of an AE is missing and the stop date either falls after the first dose of apraglutide or missing, then the AE will be considered a TEAE. When partial dates are present in the data, both a partial start date and/or a partial stop date will be evaluated to determine whether it can be conclusively established that the AE started prior to the start of apraglutide or stopped prior to the start of apraglutide. If the above cannot be conclusively established based on partial and/or present dates, then the AE will be considered TEAE.

For classification of prior and concomitant medications, the same conservative convention described above will be applied for handing missing or partial medication dates, and medications will be considered concomitant if it cannot be conclusively established whether or not they were taken at any point after the start of apraglutide.

If “Relationship to trial medication” field from the original case report forms (eCRFs) for an AE is missing, it will be imputed as “Definitely Related”.

In case of missing normal ranges for laboratory results, the normal ranges will be imputed using literature references (such as Merck, 2021) in the corresponding ADaM dataset for analysis purpose.

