MAGIC grade assessment	X	X	X	X	X	X	X	X	X	X	X	X	X
Questionnaires ¹⁵	X	X	X	X	X	X	X	X	X	X	X	X	X

ADA=anti-drug antibody; CR=complete response; CT=computed tomography; ECG=electrocardiogram; eCRF=electronic Case Report Form; EO²=end of trial; GI=gastrointestinal; MAGIC= Mount Sinai Acute Graft Versus Host Disease International Consortium; MR=magnetic resonance; PK=pharmacokinetics; NA=Not applicable

Footnotes to Table 2:

1. Follow-up visits:
 - If a complete lower GI-aGVHD response is achieved by Week 8 inclusive, follow-up visits at Weeks 8, 13, 17, 21, 26, 52, and 104 should be completed
 - If a complete lower GI-aGVHD response is achieved from Week 9 to Week 13 inclusive, follow-up visits at Weeks 13, 17, 21, 26, 52, and 104 should be completed
 - If a complete lower GI-aGVHD response is achieved during the optional treatment period or lower GI-aGVHD flare treatment, perform the next follow-up visit available after a complete lower GI-aGVHD response is achieved (for example, if a complete lower GI-aGVHD response is achieved at Week 20, perform follow-up visits at Weeks 21, 26, 52, and 104)
2. In case of early treatment discontinuation, an early treatment discontinuation visit should be performed at approximately 4 weeks (+1 week) after the last IMP dose. Follow-up starts from the early treatment discontinuation visit and the subject will then transition to Weeks 26, 52, and 104 (EOT)
3. In case of early trial discontinuation, the subject will be asked to return to the site approximately 4 weeks (+1 week) from the date of early trial discontinuation. After this visit, there will be no further visits
4. All visit procedures are recommended to be done on the same day, unless otherwise specified
5. In Germany, only colonoscopy or MR enterography will be performed (not CT colonography)
6. The Day 56 lower GI biopsy is optional and should be done only if a lower GI biopsy was done prior to apaglutide therapy and if the subject is medically suitable for the procedure
7. Vital signs (blood pressure, heart rate, temperature)
8. A phone call must be performed every 4 weeks (\pm 72 hours) between Weeks 26 and 104 to collect information regarding adverse events, concomitant medications, weight changes, and other pertinent information to assess the subject's medical condition. Phone calls will not be undertaken when the subject is attending the site for a scheduled visit

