##### 4.3.8.1 *Adverse events*

Adverse events (AEs) will be coded using Medical Dictionary for Regulatory Activities (MedDRA) version 24.0. The severity of all adverse events will be graded according to the National Cancer Institute (NCI) Common Terminology Criteria for Adverse Event (CTCAE) [NCI-CTCAE, 2017], version 5 (publication date: 27 November 2017). Adverse Events will be summarized descriptively by the frequency and incidence of subjects experiencing events corresponding to System Organ Class (SOC) MedDRA and Preferred Term (PT). Subjects with multiple occurrences of events will only be counted once at the maximum severity/grade to trial therapy for each PT, SOC, and overall. Summaries will be ordered by decreasing overall incidence in SOC; and by decreasing overall incidence of PTs within a SOC .

The overall observation period will be divided into mutually exclusive categories, including pre-treatment, on-treatment (treatment emergent), post-treatment:

- A treatment-emergent adverse event (TEAE) is defined as an adverse event with a start date and time on or after the first administration of apaglutide or having been present prior to the first dose of apaglutide but worsening in severity after starting treatment relative to the pre-treatment state. Adverse events are considered as TEAE until 28 days after the last dose of apaglutide received.
- A pre-treatment Adverse Event is defined as an AE occurring after the signature of the ICF and before the first dose.
- A post-treatment adverse event is defined as an AE occurring 28 days after the last dose.

Adverse events that are reported as possibly, probably, or definitely related to apaglutide therapy will be counted as related to trial therapy. Adverse events with a missing relationship will be considered as "related".

An overview of all Adverse Events will be provided.

All SAEs or AEs that led to withdrawal will be listed, Serious Adverse Events (SAEs) will be flagged within the listing.

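### The SAP's partial-date rule for adverse events has no test against the end of the 28-day window, so an event whose known month or year puts it wholly after that window is classed as treatment-emergent

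*SAP*

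**What the plan says.** SAP 4.1.2 (Handling of Dropouts and Missing Data) sets out the handling of incomplete adverse event dates in three steps.

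- A principle for imputation: "the missing component(s) will be assumed as the most conservative value possible, taking the worst-case approach".
- A general default: "an adverse event will be considered a treatment emergent adverse event (TEAE) unless the recorded dates conclusively prove otherwise".
- A specific instruction for partial dates. Start and stop dates are examined to see whether "it can be conclusively established that the AE started prior to the start of apraglutide or stopped prior to the start of apraglutide". If not: "If the above cannot be conclusively established based on partial and/or present dates, then the AE will be considered TEAE".

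SAP 4.3.8.1 (Adverse events) divides the observation period into mutually exclusive pre-treatment, on-treatment and post-treatment categories. It sets the upper limit: "Adverse events are considered as TEAE until 28 days after the last dose". It also defines the class beyond it: "A post-treatment adverse event is defined as an AE occurring 28 days after the last dose". Treatment-emergent and post-treatment events have separate sets of tables (SAP 4.3.8.1.2 and 4.3.8.1.3).

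**The concern.** The specific instruction looks at one end of the window only. An event known to have begun in a month well after the last dose plus 28 days can never be shown to have begun or ended before the first dose. It therefore falls through to the default and becomes a TEAE, while 4.3.8.1 makes it post-treatment. The general default in the same paragraph is not limited to the pre-dose side and would allow the recorded month to prove the event too late. Two programmers could follow the same paragraph and produce different tables.

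Safety and tolerability is the primary objective (Protocol 1.5.1.1), and the TEAE summaries by dose are central to it. The class also decides more than which table an event enters. The special-interest and particular-interest summaries (SAP 4.3.8.2 and 4.3.8.3) are specified for treatment-emergent events, and the post-treatment list in 4.3.8.1.3 has no counterpart to them. A late event of that kind would appear in those summaries under one reading and be absent under the other.

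**Working it through.** The plan states no figure here to reproduce. The check applies the written rule to example dates.

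**Inputs**

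- Last scheduled dose: Week 7 (main treatment), Week 12 (extension) or Week 25 (optional treatment), from SAP 2.1.
- Window end: last dose + 28 days, from SAP 4.3.8.1.
- Adverse events are collected from consent to the end-of-trial visit (Protocol 6), nominally Day 728 (Protocol Table 2).
- Primary Analysis cut-off: 01 Dec 2023 inclusive, later data cut by program (SAP 1).
- Planned arm size: 15 (Protocol 7.4).
- Assumed for illustration: first dose on 15 Jan 2023, and the partial start dates below.

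**Window end** = 7 × week of last dose + 28

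| Last dose | Day of last dose | Window ends | In the assumed case |
|---|---|---|---|
| Week 7 | 49 | 49 + 28 = Day 77 | 2 Apr 2023 |
| Week 12 | 84 | 84 + 28 = Day 112 | 7 May 2023 |
| Week 25 | 175 | 175 + 28 = Day 203 | 6 Aug 2023 |

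**Classification of partial start dates.** The literal rule tests only whether the latest possible start precedes the first dose. The two-sided rule also tests whether the earliest possible start falls after the window end.

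| Recorded start | Possible range | Literal 4.1.2 | Two-sided |
|---|---|---|---|
| Dec 2022 | 1–31 Dec 2022 | Not TEAE (pre-treatment) | Pre-treatment |
| Jan 2023 | 1–31 Jan 2023 | TEAE | TEAE |
| Mar 2023 | 1–31 Mar 2023 | TEAE | TEAE |
| Sep 2023 | 1–30 Sep 2023 | TEAE | Post-treatment |
| Dec 2023 | 1–31 Dec 2023 | TEAE | Post-treatment |
| 2024, month unknown | 1 Jan–31 Dec 2024 | TEAE | Post-treatment |

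The result in every row is the same for all three last-dose weeks. The readings differ only where no value of the missing component could place the onset inside the window. The September 2023 row shows that such an event can fall before the Primary Analysis cut-off. The 2024 row can reach only the end-of-trial analysis.

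**Effect of one event.** In a subject with no other event of that preferred term, one reclassified event changes the arm's incidence by 1/15 = 6.7 percentage points.

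**The case against.** The best defence is that the SAP, read as a whole, already gives the right answer. Only missing components are imputed, so a recorded month or year stands. The general default turns on what the recorded dates prove, in either direction. Section 4.3.8.1 supplies the upper limit and a post-treatment class. Derivations are also delegated to a separate analysis dataset specification (SAP 1), which is not among the documents and may settle the matter. This stands in part: the intended result is probably the two-sided one, and actual misclassification cannot be shown. But the instruction written specifically for partial dates is one-sided, and the list of changes in SAP Section 6 does not address it. The general sentence leaves the paragraph inconsistent with itself and does not cure it.

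A reader might infer more than the documents support:

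- **That every partial-date event after the window is misclassified.** It is not. Where the known part overlaps the window, TEAE is the correct cautious default.
- **That the effect is as large as the follow-up outside the window.** With follow-up to Day 728 that share is (728 − 77)/728 = 89%, (728 − 112)/728 = 85% or (728 − 203)/728 = 72%. These are shares of calendar time, not of events, and they assume two full years of observation. Protocol 1.1 cites 51.0% overall survival at 6 months in the single-arm ruxolitinib trial, so many subjects may contribute far less. Flare re-treatment up to Week 25 also moves the last dose.
- **That telephone follow-up makes missing days common.** Protocol Table 2, footnote 8, says "A phone call must be performed every 4 weeks" between Weeks 26 and 104 to collect event information. It says nothing about date precision. Serious events are reported within 24 hours with queries (Protocol 6.3.2), so late deaths and serious infections are poor examples of undated events.
- **That the date rule creates related events.** A missing relationship counts as related whatever the period, and the post-treatment tables include related events too.

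**Conclusion.** The point holds in a limited form. Followed literally, SAP 4.1.2 gives the wrong class to adverse events whose known month or year places onset wholly after the last dose plus 28 days. That conflicts with the 28-day limit and the exclusive periods of 4.3.8.1, and with the general sentence in 4.1.2 itself.

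The direction is known: TEAEs, and the treatment-emergent special-interest and particular-interest summaries, can only be over-counted, and the post-treatment tables under-counted. No event is lost from the data and no hypothesis test is affected, because the safety tables are descriptive. The total size is unknown and could be nil, since no count of partial dates is given. The 6.7-point figure is per event and assumes 15 treated subjects in the arm. Most of the exposure is in the end-of-trial analysis, though late events before 01 Dec 2023 could also enter the Primary Analysis tables. It is worth correcting because the remedy is cheap and has no real downside.

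**What to change.** Replace the last sentence of the partial-date paragraph in SAP 4.1.2 with a rule of this form:

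> An AE with a partial date is pre-treatment if its latest possible start date or its latest possible stop date is before the first dose (unless it worsened after the first dose, per 4.3.8.1); post-treatment if its earliest possible start date is more than 28 days after the last dose of apraglutide received, including any flare re-treatment; otherwise it is a TEAE.

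This keeps the cautious default for dates that are truly ambiguous, preserves the worsening clause, and uses the same last-dose reference as 4.3.8.1. The cost is one sentence in the SAP and one condition in the adverse event dataset program. It would also help to confirm which reading the dataset specification used for the Primary Analysis, and to list any partial-date events whose class changes.

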## 4.2 Analysis Sets

### 4.2.1 Full Analysis Set

The Full Analysis Set (FAS) comprises all enrolled subjects (randomized and non-randomized). All efficacy estimations will be conducted using the FAS. All subjects will be analyzed according to the apraglutide planned dose (High Dose, Low Dose, Low Body Weight Dose) and in total (Total randomized, Total).

#### 4.2.2 *Low Body Weight Analysis Set*

The Low Body Weight (LBW) Analysis Set comprises a separate, non-randomized cohort of up to four subjects with body weights ranging from 40.0 to <50.0 kg assigned to receive 2.5 mg apaglutide (LBW dose) who receive at least one dose of therapy and who provide at least one post-baseline assessment for any secondary endpoint.

#### 4.2.3 *Safety Analysis Set 1*

Safety Analysis Set (SAS1) comprises all the randomized subjects exposed to at least one dose of apaglutide. All safety analyses will be carried out on the SAS1 according to the actual dose of apaglutide received. All principal safety analyses of subjects randomized on low or high doses of apaglutide will be carried out on the SAS1. Subjects will be analyzed according to the dose level of apaglutide received.

#### 4.2.4 *Safety Analysis Set 2*

Safety Analysis Set (SAS2) comprises all the subjects included in FAS and exposed to at least one dose of apaglutide. All safety analyses will be carried out on the SAS2 according to the actual dose of apaglutide received (if a subject receives both dose levels during the course of the trial, this subject will be assigned to the High Dose group). Supportive safety analyses will be carried out on the SAS2.

When analyses are displayed in a single layout for both SAS1 and SAS2 (using a 5-column format), this document will refer to analysis on “SAS”.

### 4.3 Statistical Methodology for Final Analysis

#### 4.3.1 *Subject Disposition*

Counts and percentages of subjects who were screened (signed informed consent), discontinued early during screening (screen failures), and randomized will be summarized in total based on all screened subjects. Reasons for screening failure will also be summarized.

Counts and percentages of subjects who were randomized, dosed, discontinued early from the treatment, discontinued early from the trial, and completed the trial will be summarized by apaglutide dose levels and in total based on the FAS.

Reasons for early discontinuation from treatment and from trial will also be summarized.

#### 4.3.2 Demographic and Baseline Characteristics

Summary tables of demographics and baseline characteristics will be provided for the FAS. Continuous variables (age at screening in years, height at screening in cm, Body Weight in kg, Body Mass Index (BMI) in  $\text{kg}\cdot\text{m}^{-2}$ ) and categorical variables (gender, race, ethnicity, region, and site) will be summarized by descriptive statistics. The numbers and percentages of missing data for a variable will be reported. Regions will be derived from Site associated to the subjects and contain the following categories: Europe (including United Kingdom), North America, Rest of the World.

#### 4.3.3 aGVHD History and baseline disease characteristics

The following selected aGVHD history information will be summarized with descriptive statistics or counts and percentages of subjects in the FAS:

- Overall grade of aGVHD at diagnosis and at baseline
- Skin stage at diagnosis and at baseline
- Liver (Bilirubin) stage at diagnosis and at baseline
- Lower GI stage at diagnosis and at baseline
- Upper GI stage at diagnosis and at baseline
- Time from lower GI-aGVHD diagnosis date to randomization and whether acute lower GI-aGVHD was evaluated by biopsy (histology) after clinical GI-aGVHD diagnosis and whether biopsy results confirmed lower GI involvement of aGVHD
- Steroid refractory criteria (progression after at least 3 days of systemic Methylprednisolone (MP); failure to respond after 7 days of systemic MP; progressed to a new organ after treatment with systemic MP; failure during steroid taper)
- Time from date of diagnosis of lower GI-aGVHD to steroid refractory (days)
- Systemic steroid dose at randomization (mg/day)
- Prior aGVHD therapy and GVHD prophylaxis by preferred term. Prior aGVHD therapy and prior GVHD prophylaxis are defined as aGVHD therapy and GVHD prophylaxis taken prior to the first dose of IMP.

#### 4.3.4 History of transplant

The following history of transplant information will be summarized with descriptive statistics or counts and percentages of subjects as appropriate in the FAS:

- Donor Type (related or unrelated) and specifications

- Conditioning regimen by preferred term
- Product Type (bone marrow, peripheral blood stem cells, cord blood single units, cord blood multiple units, and other)
- Type of graft manipulation (including T-Cell depletion or other cell manipulation)
- Cytomegalovirus (CMV) status at baseline (from LB\_VIR page eCRF)
- Time from transplant to GI-aGVHD diagnosis (days)
- Time from transplant to randomization (days)

